The AZP-3601 dose may be adjusted downward at anytime as needed to maintain albumin-corrected serum calcium within the target range or for any safety concerns.

Once patients achieve a stable albumin-corrected serum calcium with the minimum doses of supplements, they will be maintained at that dose of AZP-3601.

Patients will have their serum calcium/Albumin levels measured within 5 days after any adjustment of AZP-3601 and any other time at the discretion of the investigator. The investigator will be free to perform any other serum or urine test if needed.

In addition, there may be additional and unscheduled checks for serum calcium and phosphate at the discretion of the investigator.

At any time during the study, hypercalcemia and hypocalcemia will be managed by adjustment in active vitamin D and/or oral calcium supplementation. Adjustments will be based on laboratory values including albumin-corrected serum calcium and serum phosphate as well as on symptoms and will be performed at the Investigator's judgment. As a general guidance, adjustments should be performed when calcium values are outside the target range of 7.8 to 9.0 mg/dL, ie, 1.95 to 2.25 mmol/L.

A separate titration guideline to help the investigator and to facilitate a standardized approach to dose adjustment, will be provided to the clinical site (refer to Appendix 8.3).

Study Schedule*

	1
 	
Scrooning	1/1 Infimization
JUECHIIIU	

Part C: between Day -56 (±2 days) and Day -1. During the optimization period, doses of oral calcium and active vitamin D will be adjusted to ensure a close albumin-corrected serum calcium baseline for all subjects. In addition, any serum 25-hydroxy vitamin D (native vitamin D) and/or magnesium deficiencies will also be corrected during this optimization period.

On Day -1, at the end of the optimization period, subjects will visit the clinical

Treatment period

Part C:

Main Treatment Period

On Day 1, the subjects will complete the baseline measurements and receive the first dose of AZP-3601 at the clinical site. Subjects will leave the clinical site following completion of all study assessments.

Subjects will return to the clinical site for additional visits on Day 14, Day 15, Day 16, Day 28/Early Termination (ET), and Day 29.

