5.2 Secondary

•

- To assess the PD response of AZP-3601 on maintenance of serum calcium and phosphate levels within a target range while oral calcium and active vitamin D are progressively reduced, following multiple ascending doses administered by sc injection to patients with HP (Part C, Main Treatment Period)
- To assess the PK of AZP-3601 following single and multiple ascending doses administered by sc injection to patients with HP (Part C)
- To assess the feasibility of individual titration of AZP3601 during a 2-month treatment extension period (Part C, Extension Phase) in patients with HP (ie if individual dosing across a dose range can be implemented in a safe and effective manner and can be maintained throughout the treatment period)

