EDSREP 009 T 01 G Page 10 of 53

Version Date: 26-Aug-2022

defined in previous section, with the goal of achieving or maintaining albumin-corrected serum calcium in the target range of 7.8 to 9.0 mg/dL.

The AZP-3601 dose may be adjusted downward at any time as needed to maintain albumin-corrected serum calcium within the target range or for any safety concerns.

Once patients achieve a stable albumin-corrected serum calcium with the minimum doses of supplements, they will be maintained at that dose of AZP-3601. A separate titration guideline to help the investigator and to facilitate a standardized approach to dose adjustment, will be provided to the clinical site.

Patients will have their serum calcium/Albumin levels measured within 5 days after any adjustment of AZP-3601 and any other time at the discretion of the investigator. The investigator will be free to perform any other serum or urine test if needed.

In addition, there may be additional and unscheduled checks for serum calcium and phosphate at the discretion of the investigator.

At any time during the study, hypercalcemia and hypocalcemia will be managed by adjustment in active vitamin D and/or oral calcium supplementation. Adjustments will be based on laboratory values including albumin-corrected serum calcium and serum phosphate as well as on symptoms and will be performed at the Investigator's judgment.

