14.0 Treatment Compliance and Exposure

Exposure data of study drug, collected by CRF, will be listed by subject. In Part C, exposure data of study drug, collected by diary, will also be listed by subject. If applicable, date and time of meal intake and comments will be listed.

For Part C, exposure data of study drug will be summarized by cohort for

- Dose exposure parameters separately by main treatment period and extension phase include:
 - o Total actual dose received (µg) (Sum of all doses administered)
 - Number of doses received
 - Duration of exposure (in days) = last dose date first dose date + 1
 - Dose Intensity (μg/day) = total actual dose received / duration of exposure
 - o Relative Dose Intensity (ratio) = total actual dose received / total planned dose
- Dose increases during the main treatment period include:
 - o Doses increases at Day 15 = Yes / No (doses at Day 15 versus doses at Day 1)

EDSREP 009 T 01 G Page 19 of 53

Version Date: 26-Aug-2022

- Doses increases after Day 15 = Yes / No (doses at Day 16 or later up to Day 28 versus doses at Day 1)
- Doses increases or decreases during the extension phase (versus actual dose at Day 28) include:
 - Number of patients with one increase only (without decrease)
 - o Number of patients with at least two increases (without decrease)
 - Number of patients with one decrease only (without increase)
 - Number of patients with at least two decreases (without increase)
 - o Number of patients with both increase and decrease
 - o Number of patients with no change in dose

Study drug dispensing and returning will be listed by subject.

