17.1.1 Adverse Events

A treatment-emergent adverse event (TEAE) is defined as any event not present prior to (the first) administration of the study drug or any event already present that worsens in either severity or frequency following exposure to the study drug.

An overall summary table will be provided by treatment and overall for each study part with the number of subjects and events reporting, AEs, TEAEs, treatment-emergent SAEs, treatment-emergent AEs of special interest (AESIs), and TEAEs leading study drug discontinuation.

Based on the pharmacology of AZP-3601 as well as other PTH analogs, and the pathophysiology of HP, AESIs are as follows:

- Hypocalcemia (including the following symptoms: agitation, anxiety, hypoestesia, paresthesia, muscle cramping, muscle fatigue, musculoskeletal pain, musculoskeletal stiffness, myalgia, tetany, seizure, tremor, brain fog).
- Hypercalcemia (including the following symptoms: thirst, frequent urination, abdominal pain, nausea, vomiting, fatigue).
- Hypercalciuria.
- Orthostatic hypotension and vasodilatory symptoms (including postural/orthostatic dizziness, syncope, tachycardia/palpitations).

A summary table with the number of subjects reporting TEAEs and the number of events, categorized by system organ class (SOC) and preferred term (PT) coded according to the MedDRA, will be presented by /cohort (for Part C) and overall for each study part. Subjects will only be counted once within each system organ class or preferred term.

A summary table with the number of subjects reporting TEAEs, categorized by SOC, PT and relationship to study drug (Related or Not Related), will be provided by //cohort (for Part C) and overall for each study part. A treatment-related TEAE is defined as any TEAE that is assessed by the investigator as definitely, likely, possibly or unlikely related to study treatment. TEAE that is assessed as Not Related will be defined as not treatment-related. Subjects with multiple events within a particular body system or preferred term will be counted under the category of their most drug-related event within that body system or preferred term.

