A summary table with the number of subjects reporting TEAEs, categorized by SOC, PT and severity as recorded on eCRF (Mild, Moderate, Severe, Life-threatening or Death), will also be provided by cohort (for Part C) and overall for each study part. Subjects with multiple events within a particular body system or preferred term will be counted under the category of their most severe event within that body system or preferred term.

A summary table with the number of subjects reporting treatment-emergent AESIs and the number of events, categorized by SOC and PT coded according to the MedDRA, will be presented by treatment (for Parts A and B)/cohort (for Part C) and overall per for each study part. Subjects will only be counted once within each body system or preferred term.

The following missing data will be imputed as defined (for calculations only / will not be presented):

- Missing AE severity or relationship will be assumed to be severe or related, respectively
- Missing AE start times for the determination of treatment emergence will be assumed to occur after treatment unless partial date documents the AE as happening prior to treatment
- Missing AE start date will be assumed to be after treatment for the determination of TEAE unless partial or complete end date documents the AE as happening prior to treatment

All AEs (including non-treatment-emergent events) recorded on the eCRF will be listed, with a flag to indicate whether the AEs are AESIs.

A separate listing of TEAEs leading to study drug discontinuation will be provided.

EDSREP 009 T 01 G Page 31 of 53

Protocol: AZP-3601-CLI-001 Version Date: 26-Aug-2022

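### No planned summary links adverse events to AZP-3601 dose reductions in the extension, and dose decreases are counted without a reason and against the Day 28 dose

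*SAP*

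**What the plan says.** **Dose rule.** The Protocol synopsis (Part C, Extension Phase) allows the dose to be "adjusted downward at anytime as needed to maintain albumin-corrected serum calcium within the target range or for any safety concerns". SAP 6.0 carries the same rule ("The AZP-3601 dose may be adjusted downward at any time as needed") with the same two grounds. One ground is routine titration; the other is a tolerability outcome.

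**Objectives.** Safety and tolerability in the extension is a primary objective (SAP 5.1). A secondary objective in SAP 5.2 is the feasibility of individual titration, explained as "if individual dosing across a dose range can be implemented in a safe and effective manner" and can be maintained through the treatment period.

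**Adverse event outputs.** SAP 17.1.1 plans an overall summary whose last items are "treatment-emergent AEs of special interest (AESIs), and TEAEs leading study drug discontinuation". It adds: "A separate listing of TEAEs leading to study drug discontinuation will be provided". It also plans TEAE tables by system organ class and preferred term, by relationship and by severity, a separate table of events of special interest, and a listing of all AEs with a special-interest flag. SAP 17.1 reports the main period and the extension separately.

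**Exposure outputs.** For the extension, SAP 14.0 counts patients by cohort in six categories: one increase only, two or more increases, one decrease only, two or more decreases, both directions, and no change. The stated comparator is the actual Day 28 dose. For the main period it counts increases only. Dose intensity and relative dose intensity are also summarised.

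**The concern.** Where the dose can be lowered instead of stopped, discontinuation is an insensitive marker of intolerance. Patients may have to step back from a dose because of an adverse event while the discontinuation row stays at zero. The exposure table would show that doses fell, but not whether this was calcium fine-tuning or poor tolerability. That distinction bears directly on whether individual titration was safe and could be maintained. If it is not prespecified, a reader of the report has to infer it by matching listings by hand.

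**Working it through.** The documents state no figure to reproduce, and SAP 6.1 says that no formal sample size calculation was done. The check is mainly a comparison of text.

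**1. Action-taken outputs described in the SAP text**

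| Outcome | Summary rows | Listings |
|---|---|---|
| TEAEs leading to discontinuation | 1 | 1 |
| TEAEs leading to dose reduction | 0 | 0 |
| TEAEs leading to interruption | 0 | 0 |

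**2. Dose-decrease outputs in SAP 14.0.** In the extension, three of the six categories involve a decrease (one only, two or more, both directions), and none is split by reason. In the main period there are none.

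**3. Where an event behind a reduction would appear.** If it is recorded as a TEAE, it appears in the organ class/preferred term, relationship and severity tables for the extension. It also appears in the special-interest table if it is, for example, hypercalcemia, hypercalciuria or an orthostatic/vasodilatory event. The reduction itself belongs to the exposure summary, subject to step 4. No planned summary joins the two.

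**4. The Day 28 comparator.** Take a hypothetical patient on 20 µg at Day 28 whose extension doses are 30, 40 and then 30 µg. This sequence only tests the counting rule; it uses the 10 µg increments that both documents give.

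| Dose (µg) | Minus Day 28 dose | Minus preceding dose |
|---|---|---|
| 30 | 30 − 20 = +10 | 30 − 20 = +10 |
| 40 | 40 − 20 = +20 | 40 − 30 = +10 |
| 30 | 30 − 20 = +10 | 30 − 40 = −10 |

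Read literally, the Day 28 comparison shows no decrease, so the patient falls among those with increases only. Against the preceding dose the patient belongs with those who had both. A step back from a raised dose, which is the pattern of most interest for tolerability, is the one that can drop out of the decrease counts.

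**5. Purely illustrative size.** Assume that all of the roughly 24 planned patients (2 cohorts of about 12) enter the extension, that x of them have the dose lowered for an adverse event, and that nobody stops. Exact (Clopper-Pearson) 95% intervals; for 0/24 the upper limit is 1 − 0.025^(1/24) = 14.2%.

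| Quantity | Rate | 95% CI |
|---|---|---|
| Planned row: discontinuation, 0/24 | 0% | 0 to 14.2% |
| Reduction for an AE, 2/24 | 8.3% | 1.0 to 27.0% |
| Reduction for an AE, 4/24 | 16.7% | 4.7 to 37.4% |
| Reduction for an AE, 6/24 | 25.0% | 9.8 to 46.7% |

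The values of x are invented. The table shows how far the two measures can differ, not what to expect.

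**The case against.** A reader might infer that intolerance handled by lowering the dose appears in no safety summary. The documents do not support that. Recorded TEAEs are tabulated whatever action was taken, by study phase, and the likely safety reasons for lowering a PTH analog are largely prespecified events of special interest with their own table. In the illustration, the four patients' events would be reported, and the 0/24 would be a correct count of discontinuations.

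Other points on that side:

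- **How common reductions would be.** Nothing says that intolerance would usually be handled by lowering the dose. The documents permit it, and for hyper- and hypocalcemia they describe adjustment of supplements.
- **Listings.** All AEs, and exposure from both CRF and diary, are listed by patient. With about 24 patients, events and dose changes can be compared by eye.
- **Unseen material.** The output list and table shells (SAP Appendices 3 and 4) and the eCRF are not in the reviewed text. An action-taken column or a reason-for-change field may exist there.
- **Study type.** The study is exploratory and descriptive, with no hypothesis tests.

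These points narrow the finding but do not remove it. A TEAE table shows that an event occurred and an exposure table shows that a dose changed; neither shows that one led to the other. Matching listings by date is an after-the-fact judgement, not a specified result, and the SAP body should state the rule even if the data field exists. The objection says nothing about the Day 28 comparator.

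**Conclusion.** The concern holds as a gap in linkage and counting. An analyst who follows the SAP text would produce no summary that separates reductions made for an adverse event from routine calcium titration, and on a literal reading would miss some step-downs altogether.

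It would go too far to say that the safe-titration objective is not answered. Extension TEAEs, events of special interest, laboratory data, injection site reactions and dose-change counts all bear on it. It is answered only indirectly.

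The size cannot be estimated, because the documents give no expected rate of reductions. The conclusion assumes that the unseen shells and eCRF do not already supply the link. It concerns mainly the extension, where the down-titration rule sits. The change is worth making because tolerability is primary there and the cost is small.

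**What to change.** 1. **SAP 17.1.1.** In the overall TEAE summary for Part C, mainly the extension, add a row for TEAEs leading to AZP-3601 dose reduction, and one for interruption if that is recorded. Give patients and events, by cohort and overall. Extend the discontinuation listing to these events.
2. **SAP 14.0.** Count each decrease against the immediately preceding dose, and split decreases by recorded reason: calcium control, adverse event, other. State how a decrease is classified when high calcium was also reported as an adverse event, since both reasons could then apply.
3. **Source.** Use the recorded action taken or reason for change where it exists. If only dates can be linked, label the result as temporal association, because doses may change at any time in the extension and timing alone does not establish the reason.

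The cost is SAP wording, a few table rows, a wider listing and some programming. No new assessment and no change to dosing is involved.

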6.2 Randomization

EDSREP 009 T 01 G Page 11 of 53

Version Date: 26-Aug-2022

Part C is not randomized. All patients will receive AZP-3601 and no placebo will be administered. patients will be assigned to a cohort based on their availability. After obtaining written informed consent, patients will be screened according to the inclusion and exclusion criteria. Patients will be assigned unique patient numbers allocated in ascending order within the clinical site, that identify the study site and the individual subject. The patient number will be as follows: XXX-YYY, with XXX for country and site number, and YYY for patient counter. Any replacement patient will receive the number of the patient to be replaced, increased by 500 (thus XXX-501 as replacement for XXX-001).

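### The Part C causality table pools TEAEs graded unlikely with those graded definitely, likely and possibly related; showing unlikely separately would sharpen it at little cost

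*SAP*

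**What the plan says.** SAP section 17.1.1 plans a table of subjects with TEAEs "categorized by SOC, PT and relationship to study drug (Related or Not Related"). The two categories are defined asymmetrically. On one side, the treatment-related category takes in every TEAE "assessed by the investigator as definitely, likely, possibly or unlikely related to study treatment". On the other, "TEAE that is assessed as Not Related will be defined as not treatment-related". So five investigator grades become two, and the cut falls between unlikely and not related.

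Two further rules in the same section act on this table. Subjects with several events are "counted under the category of their most drug-related event within that body system or preferred term". For missing values, "Missing AE severity or relationship will be assumed to be severe or related, respectively".

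On the setting, SAP section 6.2 says of Part C: "All patients will receive AZP-3601 and no placebo will be administered". Safety and tolerability is the primary objective (SAP section 5.1), and each of up to two cohorts has about 12 patients (SAP section 6.0).

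Two other places bear on the choice. SAP section 8.1.3 states as a general rule that categorical data are tabulated in the categories of the eCRF or database, without manipulation for presentation. The severity table in section 17.1.1 follows that approach and keeps all five recorded grades.

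**The concern.** The label Related will cover events that the investigator placed one step above not related. A reader who sees only the column heading cannot tell that it includes them.

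This matters more in Part C than it would in a controlled study. Patients start AZP-3601 while calcium and active vitamin D are being withdrawn. The symptoms listed for the adverse events of special interest include non-specific ones such as anxiety, fatigue, myalgia and nausea. Many TEAEs may therefore have plausible causes other than the drug. The relationship table is the only table described in section 17.1.1 that uses the investigator's view of cause; the listed contents of the overall AE summary include no line for related TEAEs. An all-causality table by SOC and PT is already planned, so the relationship table adds information only as far as it discriminates. Pooling unlikely into Related moves it towards the all-causality table.

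**Working it through.** The plan states no figure to reproduce: there is no sample size calculation, expected AE rate or distribution of causality grades. The check is of the text, followed by arithmetic on what the rule does to a count.

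**1. Direction.** For one SOC or PT row, let R be the number of subjects whose strongest grade is definitely, likely or possibly related (with missing relationship set to related), U the number whose strongest grade is unlikely, and N the number whose events are all not related. The subject rule makes these groups mutually exclusive.

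- Related under the SAP rule: R + U
- Related with unlikely shown separately: R
- Difference: U, which is never negative and is zero if no subject in the row has unlikely as the strongest grade

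**2. Size per subject.** SAP 8.1.3 bases percentages on subjects exposed within a treatment. With 12 in a cohort, each subject in U adds 1/12 = 8.3 points.

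| U in the row | Added to Related |
|---|---|
| 0 | 0 |
| 1 | 1/12 = 8.3 points |
| 2 | 2/12 = 16.7 points |
| 4 | 4/12 = 33.3 points |

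These values of U are assumed; the documents give none.

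**3. Effect of the subject rule.** Suppose each of 12 subjects has m independent TEAEs in the row, a share r graded possibly or higher and a share q graded unlikely. The expected Related count is 12 × [1 − (1 − r)^m] without unlikely and 12 × [1 − (1 − r − q)^m] with it. All inputs are assumed, with r = 0.10:

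| m | q | Without unlikely | With unlikely |
|---|---|---|---|
| 1 | 0 | 1.2 (10%) | 1.2 (10%) |
| 1 | 0.10 | 1.2 (10%) | 2.4 (20%) |
| 3 | 0 | 3.3 (27%) | 3.3 (27%) |
| 3 | 0.10 | 3.3 (27%) | 5.9 (49%) |
| 3 | 0.20 | 3.3 (27%) | 7.9 (66%) |

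At q = 0.10 the increase is 2.4 − 1.2 = 1.2 subjects when m = 1 and 5.9 − 3.3 = 2.6 when m = 3. Counting each subject at the strongest grade enlarges the shift when subjects have several events. This shows the mechanism and is not a forecast: few rows will have three events in every subject.

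**4. Consistency within the SAP.** Section 8.1.3 keeps eCRF categories; the severity table keeps them; the relationship table collapses five to two. The supplied text gives no reason for the difference. The eCRF causality field is not in that text, so it cannot be confirmed that the field holds exactly these five grades.

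**The case against.** The strongest defence is that the rule is explicit, pre-specified and cautious. It errs towards attribution, as does setting a missing relationship to related. That is coherent in an exploratory study with safety as its primary objective and no hypothesis testing. A specific rule in 17.1.1 may also be meant to override the general one in 8.1.3. This largely stands: the pooling is a convention, and a total that includes unlikely is a legitimate thing to report.

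A reader might infer more than the documents support:

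- *That drug effect can no longer be separated from background.* Not Related remains as a category. What prevents separation in Part C is the missing comparator, which regrouping does not supply. The lack of placebo is also specific to Part C; the Safety Set definition in SAP 9.1 refers to placebo recipients.
- *That causality is the only planned means of judging drug effect.* The SAP also plans TEAEs by SOC and PT regardless of cause, severity, events of special interest, injection site reactions, laboratory changes, serum calcium over time, and AEs in the Enrolled Set, which can include events before dosing.
- *That a headline related-TEAE rate is inflated.* The stated counts are within SOC or PT, and no overall related line is listed.
- *That dose decisions are affected.* The review between cohorts uses separate interim reports (SAP 7.2), which are not shown to use this grouping.
- *That protocol and SAP conflict.* The supplied protocol text contains no causality scale.

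The output list and table shells were not available and might show the original grades. All AEs are to be listed, but section 17.1.1 does not say that the listing carries the original grade.

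**Conclusion.** The point holds as a limited one about presentation. Pooling unlikely into Related blurs the one causality table described in section 17.1.1. Within a row it can only raise the Related count or leave it unchanged, by one subject (about 8 points of a 12-patient cohort) for each subject whose strongest grade there is unlikely. The direction follows from the definitions alone. The size depends on grade frequencies that the documents do not give, and may be zero.

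The documents do not show that the definition is an error, or that treatment-related must exclude unlikely. They show five grades reduced to two without a stated reason, in a SAP whose general rule and severity table keep the original categories. Separating unlikely while retaining the pooled figure loses nothing, because the pooled figure is the exact sum R + U.

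**What to change.** In the SOC/PT-by-relationship table of SAP 17.1.1:

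- Show three categories: Related (definitely, likely, possibly), Unlikely and Not Related. Keep the rule of counting each subject once at the strongest grade, in that order.
- Keep the pre-specified pooled count as a line labelled Related + Unlikely, so that the conservative figure stays visible.
- State that a missing relationship set to related falls in the first category.
- Reconcile sections 8.1.3 and 17.1.1, either by making the causality table follow the general rule or by stating that it is an exception and why.

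The cost is a SAP wording change, one more column and sparser cells in cohorts of about 12. No new data are needed.

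### AESIs are defined in four categories but tabulated by SOC and PT, so the number of patients with each AESI as defined cannot in general be read from the planned outputs

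*SAP*

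**What the plan says.** SAP section 17.1.1 names four AESI categories: hypocalcemia, hypercalcemia, hypercalciuria, and orthostatic hypotension with vasodilatory symptoms. Two carry long symptom lists:

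- "Hypocalcemia (including the following symptoms: agitation, anxiety, hypoestesia, paresthesia, muscle cramping, muscle fatigue, musculoskeletal pain, musculoskeletal stiffness, myalgia, tetany, seizure, tremor, brain fog": 13 symptoms.
- "Hypercalcemia (including the following symptoms: thirst, frequent urination, abdominal pain, nausea, vomiting, fatigue": 6 symptoms.

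Hypercalciuria has no symptom list, and the orthostatic and vasodilatory category has a short one.

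Three outputs in the same section deal with AESIs:

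- **Overall AE summary**, by treatment and overall for each study part. It covers "treatment-emergent SAEs, treatment-emergent AEs of special interest (AESIs), and TEAEs leading study drug discontinuation", among other counts, and so gives one AESI figure across all four categories.
- **Detailed AESI table**: "A summary table with the number of subjects reporting treatment-emergent AESIs and the number of events, categorized by SOC and PT", by cohort for Part C and overall. The counting rule is "Subjects will only be counted once within each body system or preferred term".
- **AE listing**, "with a flag to indicate whether the AEs are AESIs". The flag is described as yes or no, with no category named.

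Safety and tolerability is the primary objective for both periods of Part C (SAP section 5.1), in up to two cohorts of about 12 patients each (SAP section 6.0).

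**The concern.** The categories are defined but never used as a level of summary. The hypocalcemia list runs from psychological symptoms such as anxiety, through neurological ones such as paresthesia, to muscular ones such as cramping. One patient's AESI, or one category's patients, can therefore be spread over many rows. Patient counts cannot be added across those rows, because a patient may appear in several of them.

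In Part C, oral calcium and active vitamin D are withdrawn while the drug dose is adjusted. How many patients ran into trouble with low calcium, and how many with high calcium, are thus central safety results. With no hypothesis testing planned (SAP section 8.4.3), the descriptive counts carry the safety conclusions. A pooled AESI count merges two opposite risks.

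**Working it through.** The plan states no figure to reproduce, because this is a question of table layout. The check is whether the described outputs determine *H*, the number of patients in a cohort with any hypocalcemia AESI (the term or a listed symptom).

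**Inputs.** Cohort size *n* = 12 (SAP section 6.0). The outputs are those of SAP section 17.1.1. The event counts below are assumed for illustration, as the documents contain no data. I read the overall summary's split by treatment as a split by cohort in Part C, which is the reading more favorable to the plan.

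**Step 1: PT rows alone.** If the hypocalcemia PTs have patient counts c1, …, ck, then

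max(ci) ≤ *H* ≤ min(*n*, Σci).

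| Assumed PT counts | Lowest *H* | Highest *H* | Range, of 12 |
|---|---|---|---|
| 3, 3, 3 | 3 | min(12, 9) = 9 | 25.0% to 75.0% |
| 2, 2, 2, 2 | 2 | min(12, 8) = 8 | 16.7% to 66.7% |
| 4, 3, 2, 1 | 4 | min(12, 10) = 10 | 33.3% to 83.3% |
| 5 (one PT) | 5 | 5 | 41.7%, exact |

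**Step 2: add the pooled count.** Let *P* be the pooled number of patients with any AESI, and let the PTs of the other categories have counts dj. Then

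max(max ci, *P* − Σdj) ≤ *H* ≤ min(Σci, *P*).

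Take counts 3, 3, 3 for hypocalcemia:

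- No AESI of another category: Σdj = 0, so *H* = *P*, exactly.
- *P* = 8 and Σdj = 2: *H* lies from max(3, 8 − 2) = 6 to min(9, 8) = 8. The pooled count narrows the range but does not close it.
- *P* = 9 and two other-category PTs with 3 patients each (Σdj = 6): *H* lies from max(3, 9 − 6) = 3 to min(9, 9) = 9. The pooled count does not help.

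**Step 3: both ends can occur.** Call the hypocalcemia PTs a, b, c and the two hypercalcemia PTs x, y. Assume one event per patient per PT, and no two of the five PTs in the same SOC.

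- Dataset A: patients 1–3 each have a, b and c; patients 4–6 have x; patients 7–9 have y. *H* = 3.
- Dataset B: patients 1–3 have a and x; patients 4–6 have b and y; patients 7–9 have c. *H* = 9.

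In both, every PT row and every SOC row shows 3 patients, the pooled count is 9, and there are 5 × 3 = 15 events. The two AESI summaries agree in every AESI cell, while any-hypocalcemia is 3/12 (25.0%) in one and 9/12 (75.0%) in the other.

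The SOC rows could separate such cases if hypocalcemia PTs shared an SOC. The documents do not give the MedDRA assignments, so no general reliance can be placed on that.

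**Step 4: the listing.** The listing shows which patient had which event, so *H* can be rebuilt by hand. The described flag does not name a category, so the reader must first assign each PT to one, with the data in view.

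**The case against.** The case on the other side is substantial, and most of its parts stand as limits.

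- **The incidence is not wholly absent.** A reader might infer that the plan yields no incidence of hypocalcemia or hypercalcemia. That is not supported: the PT rows for those reported terms are readable, and hypercalciuria has no symptom list. What is missing is the term together with its symptoms.
- **The pooled count sometimes settles it.** If only one category occurs, the overall summary gives the exact number. Otherwise it caps the range.
- **The symptom lists are ambiguous.** The SAP does not say whether anxiety or nausea alone is an AESI, or only as part of a calcium event. If sites report the diagnosis, the PT row comes close to the category count. A category table that counted every non-specific symptom could overstate the risk. This stands, and the fix has to meet it.
- **SOC mixing.** A reader might infer that symptoms of different AESIs, such as paresthesia and syncope, share a SOC row. That depends on MedDRA assignments not in the documents and is not relied on here.
- **Other calcium reporting exists.** SAP section 16.2.2.1 counts patients within target and normal calcium ranges, and section 17.1.4 lists clinically significant abnormal values. The calcium risk is therefore not unreported. But the in-range counts do not separate low from high, and their numbers and percentages are specified only at Baseline, Day 14 and Day 28. Unscheduled measurements are excluded from descriptive statistics (section 8.1.5).
- **Small trial.** With about 2 × 12 = 24 patients, counts can be rebuilt from the listing. This is true, but it leaves the mapping to be chosen after the data are seen.
- **Unseen shells.** The output list and table shells (SAP Appendices 3 and 4) were not in the text available for review. They may include a category level, but the SAP text describes only SOC and PT.

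**Conclusion.** The point holds in limited form. The SAP defines four AESI categories and describes no output that counts patients by category. When AESIs of more than one category and more than one PT occur, the number of patients with each AESI as defined cannot, in general, be read from any described output. In the illustration the uncertainty is 3 to 9 of 12 patients, capped by the pooled count.

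That size rests on assumed event counts, on hypocalcemia PTs that do not share SOC rows, on listed symptoms counting as AESIs, and on shells that follow the SAP text. With a single PT in the category, or a single category occurring, there is no ambiguity.

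A reader might go further and infer an analysis error. The documents do not support that: no estimate is biased and no data are lost. It is an inexpensive improvement to the reporting of a primary safety objective.

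**What to change.** In SAP section 17.1.1:

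1. Add an AESI-category variable to the adverse event dataset (ADAE), with a PT-to-category mapping fixed before database lock. The present yes/no flag cannot produce the table by itself.
2. Tabulate treatment-emergent AESIs by category first, counting each patient once per category, with PTs beneath, by cohort, study part and overall.
3. Within hypocalcemia and hypercalcemia, show patients with the reported term separately from patients with listed symptoms only, so that non-specific symptoms do not inflate the incidence.

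The cost is one derived variable, one mapping and one table shell, with no new data. The mapping takes some judgment, since each listed symptom has to be assigned in advance.
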